3.0 Study Design

Phase 1 and Phase 2: Remote, randomized clinical trial using a 12-week, longitudinal SMART (Sequential Multiple Assignment Randomized Trial) design.

Phase 1, LEVEL 1 Randomization: Participants will be randomized to one of two conditions after completing baseline assessments: high monetary incentive and low monetary and feedback. After they are randomized to an incentive arm, they will then be randomized to either MBP or VBP. After six weeks of treatment, participants will move to level 2.

[figure not shown]
Phase 1, LEVEL 2 Randomization: Those who have made a 50% reduction to Patient Health Questionnaire-9 (PHQ-9)² scores to their assigned treatment will continue in that same treatment for 6 more weeks. Participants randomized to VBP who do not show 50% reduction in PHQ-9 scores will be randomized to either weekly VBP augmented with unlimited MBP (augmentation arm) or monthly VBP with unlimited MBP (switch arm).

Participants randomized to MBP who do not show a 50% reduction in PHQ-9 scores will be randomized to either unlimited MBP with weekly VBP (augmentation arm) or unlimited MBP and monthly VBP (minimal augmentation). The decision to switch or augment treatment after there is no response to treatment (described as a <50% change in PHQ-9 score) is based on treatment recommendations from the American Psychological Association, The

National Health Service in the UK, and the AHRQ depression guidelines. The Talkspace therapists, operating as consulting members of the study team, will complete the Clinical Global Impression – Improvement Scale after 5 weeks of treatment; if the participant does not complete a PHQ-9 in a timely manner for Level 2 randomization, this scale will be referenced for determining appropriateness for Level 2 randomization.

Phase 2, LEVEL 1 Randomization: Participants will be randomized to either MBP or weekly VBP. After six weeks of treatment, participants will move to Level 2.

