Phase 1: See Section 3.0. Randomization will be determined using www.randi2.org, an open-source web-based RCT randomizer that supports many types of algorithms (complete, biased coin, truncated randomization, block randomization, and the Wei's urn model randomization). Participants will be randomized to the first level of care using Wei's urn randomization blocking by recruitment, which adapts the probability of randomization to condition by the balance in the group assignments. This tightly controls balance while permitting randomization. Level 1 participants who respond to treatment will continue in their baseline condition. Level 1 participants who do not respond to treatment by week 5 (PHQ-9 score > 50% of baseline PHQ-9 score, or CGI-I score >2) will be re-randomized to receive MBP and supplemental weekly or monthly VBP.

Phase 2: See Section 3.0. Baseline Level 1 randomization to MBP or VBP occurred on REDCap and will be triggered by a research coordinator upon enrollment. We will use simple randomization with pre-specified and concealed blocks by therapist. Level 2 randomization will occur on REDCap. Level 1 participants who respond to treatment will continue in their baseline condition. Level 1 participants who do not respond to treatment by week 5 (PHQ-9 score > 50% of baseline PHQ-9 score, or CGI-I score >2) will be re-randomized to receive MBP and supplemental weekly or monthly VBP.

Treatment Procedures: All procedures described here are methods developed and used by Talkspace, unless otherwise specified. There are four interventions in this study: Level 1 interventions are unlimited MBP and weekly VBP. Level 2 interventions are MBP with monthly VBP, and MBP with weekly VBP. After participants give consent to participate, they will be randomized to one of the two Level 1 conditions. As per Talkspace's model, participants are offered a choice of three therapists, based on the state the therapist is licensed in. Procedures for consumer/clinician initiation are the same for each treatment option. Participants can contact their therapists any time after they are provided with choices. Once participants reach out to a therapist, therapists connect within 15 minutes to 24 hours, depending on the time of day the participants made their choice and the therapists' office

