5.2 Study Assessments

Baseline Assessments:

- Demographics
- MDE Screener

- 9-item Patient Health Questionnaire (PHQ-9)
- 8-item Neuro-Quality of Life v1.0 (Neuro-QOL) Ability to Participate in Social Roles and Activities short form (Phase 2 only)
- 7-item Generalized Anxiety Scale (GAD-7)
- NIAAA Alcohol Screening Test
- IMPACT Assessment of Mania and Psychosis
- Self-reported health and health concerns
- Use of other apps and mental health treatment
- Participant Top Issue & Follow-Up Question (Phase 2 only)
- Perceived Stress Scale (Phase 2 only)
- Past Mental Health Treatment Experiences (Phase 2 only)
- Random Assignment Level 1 Reaction Questions (Phase 2 only)

Daily Assessments: Participants will be asked to answer brief, daily questions intended to capture information on daily fluctuations in mood, social and physical activity, and sleep.

Weekly Assessments:

- 9-item Patient Health Questionnaire (PHQ-9)
- 8-item Neuro-Quality of Life v1.0 (Neuro-QOL) Ability to Participate in Social Roles and Activities short form (Phase 2 only)
- 7-item Generalized Anxiety Scale (GAD-7)
- Patient Global Improvement Scale
- Major Life Event & Impact on Treatment (Phase 2 only)
- Participant Top Issue & Follow-Up Question (Phase 2 only)
- Therapist Contact Weekly Question

Week 1: Treatment Rationale Scale

Weeks 2 and 7: Credibility Expectancy Scale (Patient's Version) (Phase 2 only)

Weeks 4, 8, and 12:

- Major Life Changes
- Satisfaction with Care
- Perceived Stress scale (Phase 2 only)

Weeks 4 and 10:

- Experience of Care and Health Outcomes Survey (ECHO)
- Working Alliance Inventory-Short Revised (WAI-SR)

Week 12: Exit survey.

Early exit survey: Early drop out participants will be asked to complete a 1-question early exit survey (Phase 2 only).

Talkspace data: Talkspace meta-data (number of text interactions, time texting, time between texts, number of sessions) and content data including transcripts are collected on the Talkspace platform. All identifiable information (e.g., names, usernames, links) are scrubbed from the transcripts by an automated process internal to Talkspace prior to transfer to UW. Additionally, we will collect data on treatment intensity from Talkspace's electronic record of patient contact, which consists of time spent in treatment, number of sessions/messages over 12 weeks, and treatment attendance.

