1. Test effectiveness of unlimited daily, message-based psychotherapy (MBP) for depression, compared to weekly traditionally delivered, videoconferencing-based psychotherapy (VBP). Level 1 conditions: unlimited MBP and weekly VBP.
2. Develop an evidence-based treatment sequence for those who do not respond to either MBP or VBP. Level 2 conditions for participants who do not respond to treatment: MBP+VBP_{weekly} (switch from MBP to weekly VBP with MBP), MBP+VBP_{monthly} (switch from MBP to monthly VBP with MBP), VBP_{weekly}+MBP (switch from VBP to weekly VBP with MBP), and VBP_{monthly}+MBP (switch from VBP to monthly VBP with MBP).

Hypothesis 1: Compared to those randomized to weekly video care at baseline, patients randomized to message-based care will have greater improvements in depression (1a) and social functioning (1b), be more likely to show a treatment response (1c), and be more likely to experience remission (1d) at 5 and 12 weeks of care. Hypothesis 2: For those who fail to respond to treatment from baseline to 5 weeks, those re-randomized to receive (or retain) weekly video care will have greater improvements in depression and be more likely to show a response to treatment than those randomized to monthly video care. Hypothesis 3 (moderator): Baseline anxiety will moderate improvement in depression such that those with greater anxiety will have better response to message-based care at 5 and 12 weeks than to video-based care. Exploratory Aims: Exploratory evaluation of differences among groups in treatment engagement by week 5, ratings of therapeutic alliance at weeks 4 and 10, ratings of

quality of care and amount helped by treatment at week 10, and ratings of goal satisfaction, plans to continue using treatment, and likelihood to recommend treatment to others at week 12.

Sample Size and Power: We propose to screen 4,789 potential participants, anticipating we will enroll 1,250 participants to arrive at a final sample of 1,000 evaluated participants, assuming a 20% dropout rate by the last assessment. In our previous psychotherapy studies, dropout rates have been on the order of 10% by final assessment. In our recent on-line studies with Google Verily, drop out has been on the order of 20%. Our large incentive arm, tested in Phase 1, is based on the incentive analyses done on the Baseline Mood Study at Verily.

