Statistical Analyses: See Table 2 for analyses by hypothesis. Treatment disengagement, treatment response, and remission will be analyzed using chi-square tests and Cramér V effect sizes. 2-level linear mixed effects models using full information maximum likelihood (FIML) and an unstructured covariance matrix with client nested within clinician will be used for analyses at a single timepoint. Models predicting binary outcomes at a single timepoint will be evaluated using 2-level logistic regression models with Cholesky factorization with client nested within clinician, with Level 2 condition as the independent variable. Effect sizes for these models will be computed via pooled standard deviations of conditions at that timepoint.

Models assessing changes across time will be evaluated using 3-level mixed effects regression models with timepoint nested within client nested within clinician using FIML and an unstructured covariance matrix. Client-level effects will be allowed to randomly vary, and clinician will be a clustering variable with condition approximately balanced within clinicians. Analyses with time from baseline to week 12 will include a spline variable to account for differences in outcome trajectories from baseline to week 5 and from week 6 to week 12.

The mixed-effects models will utilize all available data. Prior research has demonstrated equivalence of longitudinal mixed model analyses using imputed versus non-imputed data (e.g., between multiple imputation and FIML).¹³ Theoretically, there is no reason to expect substantial differences between FIML and MI with a reasonable sample size and complete predictors.¹⁴ Thus, missing data will not be imputed. Cohen's *d* clinical outcome effect sizes for the model predicting PHQ-9 scores by Level 2 condition from weeks 6 to 12 will be computed as the difference between model-estimated means divided by the pooled standard deviations when the second condition

was assigned at week 6. All remaining clinical outcome effect sizes will be computed as the difference between model-estimated means divided by the pooled baseline standard deviations.

We will use the Benjamini-Hochberg procedure to account for Type 1 error by adjusting for familywise error within hypothesis families (e.g., within Hypotheses 1a to 1d; within Hypothesis 2). *P* values and effect sizes with 95% confidence intervals will be reported, as appropriate.¹⁵

Table 2. Analyses by Hypothesis

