Hypothesis	Timepoint(s)	Statistical Test	Contrast/analysis of interest
1a: Compared to those randomized to weekly video care at baseline, patients randomized to message-based care will have greater improvements in depression	Baseline to W5	3-level mixed effects model	MBP vs VBP
1b: Compared to those randomized to weekly video care at baseline, patients randomized to message-based care will have greater improvements in social functioning	Baseline to W12	3-level mixed effects model	MBP vs VBP
1c: Compared to those randomized to weekly video care at baseline, patients randomized to message-based care will be more likely to show a treatment response at 5 and 12 weeks of care.	Between W3 to W5 / W12	Chi-square tests	MBP vs VBP
1d: Compared to those randomized to weekly video care at baseline, patients randomized to message-based care will be more likely to experience remission at 5 and 12 weeks of care.	Between W3 to W5 / W12	Chi-square tests	MBP vs VBP
2: For those who fail to respond to treatment from baseline to 5 weeks, those re-randomized to receive (or retain) weekly video care will have greater improvements in depression than those randomized to monthly video care	W6 to W12	3-level mixed effects model with time centered at week 6	MBP+VBP _{weekly} vs MBP+VBP _{monthly} ; VBP _{weekly} +MBP vs VBP _{monthly} +MBP
2: For those who fail to respond to treatment from baseline to 5 weeks, those re-randomized to receive (or retain) weekly video care will be more likely to show a response to treatment than those randomized to monthly video care	W12	Chi-square test	MBP+VBP _{weekly} vs MBP+VBP _{monthly} ; VBP _{weekly} +MBP vs VBP _{monthly} +MBP
3 (moderator): Baseline anxiety will moderate improvement in depression such that those with greater anxiety will have better response to message-based care at 5 and 12 weeks than to video-based care.	Baseline to W12	3-level mixed effects model, with mean-centered baseline GAD-7	MBP vs VBP

Exploratory: We will explore whether there will be differences among groups in treatment engagement by week 5	Between W3 to W5	Chi-square test	MBP vs VBP
Exploratory: We will explore whether there will be differences among groups in ratings of therapeutic alliance	W4 / W10	2-level mixed effects models	W4: Level 1 conditions (MBP vs VBP); W10: Level 2 conditions (MBP vs VBP; MBP+VBP _{monthly} vs MBP+VBP _{weekly} ; VBP _{monthly} +MBP vs VBP _{monthly} +MBP)

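### Quality of care and amount helped are analysed only at week 10, after step-up, although week-4 ratings are most likely collected and would compare the full randomized message and video arms

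*Combined protocol and SAP*

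**What the plan says.** All references are to the combined protocol and SAP.

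- **Collection.** Section 5.2 lists "Experience of Care and Health Outcomes Survey (ECHO" and the Working Alliance Inventory together, at weeks 4 and 10.
- **Analysis times.** The Exploratory Aims in Section 8.0 take "ratings of therapeutic alliance at weeks 4 and 10", but "quality of care and amount helped by treatment at week 10" only.
- **Contrasts.** Table 2 has a row for alliance ("We will explore whether there will be differences among groups in ratings of therapeutic alliance") with the contrasts "W4: Level 1 conditions (MBP vs VBP); W10: Level 2 conditions". The week-10 set is MBP versus VBP, plus comparisons of the re-randomized groups within each Level 1 arm. The last of these names the monthly group on both sides; I read it as weekly against monthly, as in the week-12 row.
- **Step-up.** Section 3.0 says, in the same terms for both phases, "After six weeks of treatment, participants will move to level 2". Under Randomization, Section 5.1 says "Level 1 participants who respond to treatment will continue in their baseline condition", while non-responders by week 5 are re-randomized to messaging plus weekly or monthly video.
- **Model.** Section 8.0 specifies a 2-level linear mixed model with an "unstructured covariance matrix with client nested within clinician will be used for analyses at a single timepoint", and a 2-level logistic model for binary outcomes. Neither names a covariate.

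**The concern.** Two sets of ratings that appear to share a schedule are treated differently, and no reason is given. For alliance, the plan uses week 4 to compare the Level 1 conditions and week 10 to compare the Level 2 conditions. For quality of care and amount helped, it keeps only the later time.

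Week 4 is the time at which the Level 1 question has a direct randomized answer, because all participants are still assigned to one modality. By week 10 the non-responders in both arms have been assigned both modalities. What is at stake is whether the trial can say how patients rate message-based against video-based care across the full randomized arms.

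A smaller matter is precision. A week-4 rating precedes re-randomization, so it is a natural covariate for the week-10 weekly-versus-monthly contrasts. None is named.

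**Working it through.** **1. Is the measure ECHO?** The aim names no instrument. Section 5.2 places ECHO at weeks 4 and 10. The separate Satisfaction with Care measure is at weeks 4, 8 and 12, so it does not fit a week-10 analysis. Every patient-rated instrument that Section 5.2 schedules at week 10 (the weekly set, ECHO and the alliance inventory) is also scheduled at week 4. So week-4 data should exist even if one of the items comes from another of these instruments.

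**2. What would a week-10 MBP versus VBP contrast compare?**
- By Level 2 condition, as in the alliance row: participants who kept their first treatment, that is, responders. They are selected on an outcome after randomization, and Hypothesis 1c expects that outcome to differ by arm.
- By Level 1 assignment: the full randomized arms, but the comparison is of treatment sequences, since non-responders in both arms now have combined care.

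Neither compares the full arms while all are assigned to a single modality. Week 4 does.

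**3. The plan's own power figures.** Inputs from Section 8.0: 0.20 SD with more than 80% power (Level 1); 1,250 enrolled, 20% dropout, 1,000 evaluated; 324 at Level 2 with 80% power for 0.32 SD. Two-sided alpha 0.05 and equal allocation are my assumptions. With effects in SD units, power = Φ(δ/√(2/n) − 1.96).
- Level 1, n = 500 per arm: 0.20/√(2/500) = 3.162; Φ(1.202) = 88.5%, consistent with the plan.
- Level 2, n = 162 per group: 0.32/√(2/162) = 2.88; Φ(0.92) = 82.1%, close to the stated 80%.
- 1,000/0.8 = 1,250, as stated.

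The plan gives no figure for the care-quality outcome, and the point does not depend on one.

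**4. Detectable differences at 80% power.** Formula: (1.960 + 0.842) × √(1/n₁ + 1/n₂), for a continuous score.

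| Contrast | Group sizes | Detectable difference |
|---|---|---|
| Week 4, MBP vs VBP, 1,000 rated | 500 vs 500 | 0.18 SD |
| Week 4, MBP vs VBP, 1,250 rated | 625 vs 625 | 0.16 SD |
| Week 10, unswitched MBP vs unswitched VBP | 338 vs 338 (1,000 − 324 = 676, equal split assumed) | 0.22 SD, in selected groups |
| Week 10, weekly vs monthly within one Level 1 arm | 81 vs 81 (324/4, equal split assumed) | 0.44 SD |

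**5. Week-4 score as covariate in the weekly-versus-monthly contrasts.** Adjustment multiplies the residual SD by √(1 − r²). The documents give no correlation r, so a range is shown, for 81 vs 81.

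| r (assumed) | Variance removed (r²) | Detectable difference | Power at 0.32 SD |
|---|---|---|---|
| none | 0% | 0.44 SD | 53% |
| 0.3 | 9% | 0.42 SD | 57% |
| 0.5 | 25% | 0.38 SD | 65% |
| 0.7 | 49% | 0.31 SD | 81% |

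**The case against.** The aim is exploratory. No hypothesis, power claim or decision hangs on it, and analysing one of two collection times is a permissible choice. That stands, and it keeps the severity low.

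Several further objections limit what may be claimed:

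- **The week-10 analysis is not fully visible.** The Table 2 text I worked from has no row for quality of care or amount helped, and one may have been lost in conversion. A reader might infer that the plan forgot the outcome or rules out adjustment. The documents do not support either: the text is silent on covariates, and I rely only on the aims sentence. That its week-10 contrasts follow Level 2 condition is by analogy with the alliance and week-12 rows.
- **The unadjusted weekly-versus-monthly contrasts are not biased.** They compare re-randomized participants and are valid as they stand. Adjustment buys precision only.
- **The precision gain is uncertain.** The correlation is assumed. The week-4 score rates one modality and the week-10 score a combination, so a low value is plausible. The r² formula also applies to linear models, not to binary ratings.
- **A week-4 covariate costs cases if handled naively.** Section 8.0 does not impute and supports that choice by reference to complete predictors. A missing week-4 score would drop the participant.
- **Week 4 may not be message-only against video-only in strict terms.** Section 5.1 says therapists must offer a complementary live video session, historically used by 24% of patients. If that applied in the MBP arm, some would have had video by week 4. The contrast is still randomized, but by assigned condition.

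A reader might also infer that 32% of participants have changed treatment by week 10. The 324 is an expected analysis sample whose denominator is not stated: it is 32% of 1,000 and 26% of 1,250.

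**Conclusion.** The point holds as a low-severity gap in an exploratory analysis. As the aims are written, nothing compares the full randomized Level 1 arms on quality of care or amount helped before step-up, although the schedule very probably supplies the data and the plan already does this for alliance. The contrast left out could detect about 0.18 SD at 80% power, given 1,000 ratings, a continuous score, equal arms and two-sided alpha 0.05.

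The covariate is a separate and lesser improvement. In a single Level 1 arm it would lower the detectable difference from 0.44 SD to between 0.42 and 0.31 SD, for assumed correlations of 0.3 to 0.7.

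The conclusion rests on the inferred link to ECHO, or at least on the item coming from an instrument given at both weeks. It does not extend to Hypotheses 1 to 3 or to the validity of the weekly-versus-monthly contrasts.

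**What to change.** 1. **Add a week-4 contrast.** Name the instrument and items for quality of care and amount helped. Add to Table 2 a week-4 MBP versus VBP comparison by Level 1 condition, in the 2-level model used for week-4 alliance, or the 2-level logistic model if an item is binary. The cost is one table row and no new data. The families that Section 8.0 gives as examples for the Benjamini-Hochberg procedure (Hypotheses 1a to 1d; Hypothesis 2) are unaffected. It should be written in before the data are analysed, so that it is prespecified.
2. **Use the week-4 score for precision (optional).** In the week-10 weekly-versus-monthly contrasts among re-randomized participants, for alliance and for continuous care-quality scores, adjust for the participant's own week-4 score. Do not use it in any MBP versus VBP contrast: week 4 follows Level 1 randomization, so the score may itself reflect the treatment being compared.
3. **Keep everyone in.** Either model weeks 4 and 10 jointly under FIML, so that a participant with only one rating still contributes, or apply a simple fill-in for the missing covariate that ignores Level 2 assignment. The cost is a sentence of specification and a slightly larger model.

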Level 1 Power: For the quantitative primary outcome (PHQ-9) we have greater than 80% power to detect a 0.20 standard deviation across groups which corresponds to a clinically meaningful small difference. For a binary success indicator, we will consider a 50% reduction in PHQ-9 from baseline to week 5, and we have greater than 80% power to detect an absolute difference of 10% (e.g., 60% of subjects with >50% improvement versus 70% of subjects with >50% improvement).

Level 2 Power: The primary comparison in the second stage is the comparison of the Ultimate Plan (UP; MBP with weekly VBP) versus the Premium Plan (PP; MBP with monthly VBP) for each of the first stage randomization groups (MBP and VBP). We expect a second stage analysis sample of 324 subjects, and this corresponds to 80% power to detect a 0.32 standard deviation difference across the UP and PP groups when pooling across the primary MBP and VBP strata. Our primary second stage analysis will construct an overall UP versus PP difference stratifying on first stage randomization, and secondary analysis will consider the UP versus PP difference within the MBP and VBP groups separately.

Accounting for Provider Effects: Each provider will treat both MBP and VBP patients. Therefore, our primary analyses will all cluster on provider either using linear mixed models or generalized estimating equations to yield valid statistical inference. However, since treatment condition will vary within provider, the impact of provider clustering is to effectively balance or control for provider effects. Therefore, our power calculations are conservative since they do not account for the potential increase in precision associated with control for provider effects. Such within-provider randomization is in contrast to traditional cluster randomized trials where providers treat all patients in one study condition and thus increase variability associated with treatment comparisons through the well-known intra-cluster correlation coefficient.

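### Table 2 leaves out the pooled weekly-versus-monthly contrast that the power section names as the primary Level 2 analysis, so the stated 80% power belongs to a test the table does not list

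*Combined protocol and SAP*

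**What the plan says.** All the relevant text is in section 8.0 of the combined protocol and SAP.

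- **Level 2 Power, primary analysis.** "Our primary second stage analysis will construct an overall UP versus PP difference stratifying on first stage randomization".
- **Level 2 Power, secondary analysis.** "secondary analysis will consider the UP versus PP difference within the MBP and VBP groups separately".
- **Level 2 Power, sample size.** "We expect a second stage analysis sample of 324 subjects".
- **Level 2 Power, power claim.** For a sample of that size the plan states: "this corresponds to 80% power to detect a 0.32 standard deviation difference across the UP and PP groups when pooling across". The pooling meant is over both Level 1 arms.
- **Level 2 Power, opening sentence.** This describes the primary UP-versus-PP comparison as one made "for each of the first stage randomization groups (MBP and VBP".
- **Statistical Analyses.** "See Table 2 for analyses by hypothesis".
- **Table 2, Hypothesis 2.** There are two rows, PHQ-9 from week 6 to week 12 and response at week 12. Both give the same contrasts: "MBP+VBP _{weekly} vs MBP+VBP _{monthly} ; VBP _{weekly} +MBP vs VBP _{monthly} +MBP". No row of Table 2 contains a pooled weekly-versus-monthly contrast, and neither Hypothesis 2 row marks a contrast as primary or secondary.
- **Multiplicity.** Benjamini-Hochberg is to be used, "adjusting for familywise error within hypothesis families", and Hypothesis 2 is given as one such family.

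**The concern.** The power section and Table 2 prescribe different tests for the same hypothesis. An analyst following the power section runs one stratified pooled comparison. An analyst following Table 2 runs two separate comparisons, each on roughly half the non-responders, and never runs the test named as primary. The opening sentence of Level 2 Power leans towards the second reading, although the rest of that paragraph supports the first.

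Hypothesis 2 is the plan's test of the second randomisation, so three things depend on the answer:

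- which result decides the weekly-versus-monthly question;
- whether the stated 80% power describes that result;
- how many tests enter the Benjamini-Hochberg family.

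Two weaker tests can also easily disagree when the true effect is the same in both arms. Such a split could be misread as showing that the better sequence depends on the starting treatment. If the plan is left as it is, one pooled test or two separate tests could be chosen after the results are known.

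**Working it through.** **Inputs from the plan (Level 2 Power).** 324 re-randomised participants, a difference of 0.32 SD, and 80% power when pooled.

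**Assumptions, not stated in the plan.** Two-sided alpha of 0.05, 1:1 re-randomisation, and an even split of the 324 over the two Level 1 arms. This gives 162 per group pooled, or 81 per cell within an arm. The test is a two-sample comparison of means.

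**Formula.** With n1 and n2 per group, the noncentrality is δ = 0.32 / √(1/n1 + 1/n2). Power is the probability that a noncentral t with n1 + n2 − 2 degrees of freedom exceeds the two-sided critical value.

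**Step 1: the plan's own figure.** For 162 versus 162, δ = 0.32 × √81 = 2.88, the critical value is 1.967 and power is 81.9%. Power of 80% is reached at 0.312 SD. The stated 80% at 0.32 SD is thus roughly reproduced, slightly on the cautious side, and on the pooled comparison. A one-sided 0.05 test would give about 89%, so two-sided fits better.

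**Step 2: the contrasts Table 2 lists, on the same basis.**

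| Comparison | n per group | Power at 0.32 SD | SD difference for 80% power |
|---|---|---|---|
| Pooled | 162 / 162 | 81.9% | 0.312 |
| Within arm, even split | 81 / 81 | 52.6% | 0.443 |
| Within arm, larger stratum (185) | 92 / 93 | 58.1% | 0.414 |
| Within arm, smaller stratum (139) | 69 / 70 | 46.5% | 0.479 |

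For 81 versus 81, δ = 0.32 × √40.5 = 2.04 and the critical value is 1.975. The uneven split uses the illustrative 60% and 70% response rates under Level 1 Power. Non-response is then 40% and 30%, so 324 × 40/70 = 185 and 324 × 30/70 = 139.

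**Step 3: agreement between the two contrasts.** Suppose 0.32 SD is true in both arms, the strata are independent and nothing is adjusted for multiplicity.

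- Both significant: 0.526² = 0.28.
- Exactly one significant: 2 × 0.526 × 0.474 = 0.50.

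**Step 4: sample size for 80% within each arm at 0.32 SD.** The smallest n is 155 per cell, so 4 × 155 = 620 non-responders against the 324 expected.

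**Step 5: multiplicity.** Table 2 implies four Hypothesis 2 tests (two contrasts for each of two outcomes). Under Benjamini-Hochberg at 0.05, a test with p ≤ 0.05/4 = 0.0125 is always rejected and one with p > 0.05 never is. Power per PHQ-9 contrast (81 versus 81) therefore lies between its power at 0.0125, about 32%, and the unadjusted 53%. Simulation gave about 39% to 44% when each response test was assumed to have 25% to 53% power and a correlation of 0 to 0.7 with the PHQ-9 test. Those inputs are assumptions. The plan gives no Level 2 response rates, so the power of the response tests cannot be derived.

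**The case against.** The strongest reply is that the plan already names its primary test. Level 2 Power uses the words primary and secondary explicitly, and nothing in Table 2 reverses that ranking. Apart from marking exploratory rows, the table ranks no contrasts for any hypothesis. Hypothesis 2 is itself worded as a single weekly-versus-monthly comparison among all non-responders, both in the text and in the table's hypothesis column. The opening sentence can be read as loose wording that the next sentences clarify. On this view the table is merely incomplete.

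Much of that stands. It makes the pooled contrast the likelier intention, and it is why the main fix is to complete the table. It does not remove the conflict. The analysis text makes Table 2 the reference for the analyses by hypothesis, and the table lists the secondary contrasts while omitting the primary one.

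A second reply is that 53% is not the power of the three-level mixed model in Table 2. This is correct. As an illustration with assumed values, suppose adjustment for an earlier PHQ-9 correlated 0.3, 0.5 or 0.7 with the outcome reduces the residual SD by √(1 − r²). The 81-versus-81 contrast then has about 56%, 65% or 81% power. The plan gives no correlation from which to choose. The same gain would also raise the pooled test, so the loss from splitting remains. The Benjamini-Hochberg range is likewise driven by its inputs: with response-test power anywhere from 5% to 80%, simulation gives about 36% to 48%.

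**Conclusion.** The concern holds, and the plan should be corrected. The test declared primary for Level 2 does not appear in Table 2, and the stated 80% power applies only to that unlisted test. The 80% figure is sound for the pooled contrast (82% on recalculation).

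If Table 2 governs, each PHQ-9 contrast has about 53% power at 0.32 SD with an even split, or 58% and 47% with the uneven split, before any multiplicity adjustment. These figures rest on a two-sided 0.05 test, 1:1 re-randomisation and a simple comparison of means. They show the loss on the plan's own apparent basis and are not the power of the mixed model. The mismatch between the power section and Table 2 depends on none of these assumptions.

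**What to change.** 1. In both Hypothesis 2 rows of Table 2, add the weekly-versus-monthly contrast among all re-randomised participants, stratified by or adjusted for Level 1 arm, and label it primary.
2. Label the two within-arm contrasts in those rows secondary, in line with Level 2 Power.
3. Reword the opening sentence of Level 2 Power so that it describes the pooled, stratified comparison.
4. State which of these tests belong to the Hypothesis 2 family for Benjamini-Hochberg.

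If the within-arm contrasts are in fact intended as primary, change the sentence that names the primary second-stage analysis and restate the Level 2 power. On the plan's present basis that is about 53% at 0.32 SD, with 80% at about 0.44 SD, before multiplicity adjustment. A calculation for the mixed model itself, with its assumed correlations stated, would be better.

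The cost is SAP wording only: one contrast added to two table rows, labels, one corrected sentence and a line on the test family. No additional patients or data are needed.
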